3.5. Multicenter Studies

To investigate potential regional influence on efficacy, region (Japan, US including Mexico, and Europe including Israel) will be used as a stratification factor in primary and secondary efficacy analysis.

3.6. Multiple Comparisons/Multiplicity

As this is a phase 2 exploratory study, no multiplicity adjustment will be made for the analyses.

3.7. Patient Disposition

Reasons for screen failure as reported by investigators will be summarized.

A listing of final study disposition and a listing of randomized treatment assignment (planned treatment) for all randomized patients will be provided. Final study disposition and study drug disposition for all randomized patients will be summarized by planned study treatment.

3.8. Patient Characteristics

A listing of patient demographics will be provided for all randomized patients. All demographic and baseline clinical characteristics will be summarized by study treatment for all randomized patients. Baseline demographic and clinical characteristics of special interest include but not limited to:

- age (years)
- sex (female, male)
- race
- ethnicity
- weight (kg)
- BMI (kg/m²)
- waist circumference (cm)
- T2DM status (yes, no)
- country,
- liver fat content (%)
- NAS score
- fibrosis stage
- steatosis
- lobular inflammation
- hepatocellular ballooning
- ALT
- AST
- HbA1c
- CAP (TE), and
- LSM (TE).

3.9. Treatment Exposure and Compliance

A listing of patients randomized but not receiving study treatment will be provided, if applicable. The listing will include patient identification, randomized treatment arm, and the reason for not receiving study treatment, if the data is available.

A listing of randomized patients who inadvertently received incorrect study treatment anytime during the study will be provided, if applicable. The listing will include patient identification, randomized treatment arm, and information related to the treatment incorrectly received: incorrectly received study treatment, start and stop dates during which the incorrect treatment was received.

Summary of duration of follow-up (defined as time in days from date of randomization to date of the safety follow-up, date of early study discontinuation or date of death) and duration on study treatment (defined as time in days from date of first dose of study treatment to date of last dose of study treatment plus 7 days) will be provided by treatment.

3.9.1. Compliance to Study Treatment

The number of patients prematurely discontinuing study treatment prior to the 52-week visit will be provided by study treatment arms. Reasons for prematurely discontinuing study treatment prior to the 52-week visit will be provided by study treatment. Time-to-event analysis of premature study treatment discontinuation will be conducted.

If data warrants, the counts and percentages of participants who follow the planned escalation scheme, have dose interruption, or have dose de-escalation will be summarized for each treatment group. In addition, the proportion of participants with missing dosing information, receiving no LY dose, receiving 2.5 mg, 5 mg, 7.5 mg, 10 mg, 12.5 mg, or 15 mg may be presented by randomized treatment and time intervals from first dose.

Overall treatment compliance will be defined as taking at least 75% of the scheduled tirzepatide doses. Compliance will be calculated by taking the number of doses administered (regardless of the actual dose in mg administered) divided by the total number of doses expected to be administered, and then multiplied by 100. Overall treatment compliance will be summarized descriptively by treatment using the mITT population.

3.10. Concomitant Therapy

Prespecified concomitant medications of interest will be summarized by treatment at randomization. Additionally, medications of interest initiated after randomization will be summarized. Concomitant therapies will be mapped using the World Health Organization Drug Dictionary in the clinical trial database and will be further classified using Anatomic-Therapeutic-Chemical codes for reporting purposes.

Concomitant medication summaries of interest include:

- baseline antihypertensive therapy, by type
- baseline lipid lowering therapy, by type
- baseline glucose lowering medications (including TZDs)
- baseline vitamin E
- changes to baseline medication in post randomization (in term of type/class and dose):
 - antihypertensive therapy
 - lipid lowering therapy
 - glucose lowering medications (including TZDs)
 - vitamin E
- utilization after randomization of:
 - antihyperglycemic rescue therapy for hyperglycemia for participants who have T2DM at baseline, and antihyperglycemic medication for the treatment of diabetes for participants who develop T2DM during the study (antihyperglycemic medication for the treatment of prediabetes is not allowed pre protocol)
 - antidiarrheal medication, and
 - antiemetic medication.

3.11. Efficacy Analyses

The assessment of the primary, secondary and exploratory endpoints will be guided by the “efficacy” estimand. Analyses relative to the “efficacy” estimand will be conducted using the EAS without imputation of missing data. For exploratory purposes, and in the event of patients dropping out before Week 36, primary and key secondary efficacy analyses may be repeated using the EXAS guided by the “efficacy” estimand.

For informational purposes, the analysis of primary and key secondary endpoint may be repeated to be guided by the “treatment-regimen” estimand, which represents the efficacy irrespective of adherence to investigational product. Analyses relative to the “treatment-regimen” estimand will be conducted using the FAS. In this case, missing postbaseline measures will be imputed according to Section 3.11.1.3.

3.11.1.1. The Analysis Relative to the Efficacy Estimand

The analysis related to efficacy estimand will be conducted utilizing the NASH resolution with no worsening of fibrosis (Yes/No) at 52 weeks in the EAS. Logistic regression will be used to evaluate performance of each tirzepatide arm compared to placebo. The test will adjust for stratification factors by including baseline T2DM status (Yes/No) and the region (Japan, US including Mexico, and Europe including Israel).

With the aid of the logistic regression, p-values of the test as well as 2-sided 95% CI of the odds ratio for the proportion of patients achieving NASH resolution with no worsening of fibrosis at 52 weeks between each dose of tirzepatide 5 mg, 10 mg, and 15 mg and placebo will be derived.

3.11.1.2. The Analysis Relative to the Treatment-Regimen Estimand

The analysis related to treatment-regimen estimand may be conducted utilizing the NASH resolution (Yes/No) with no worsening of fibrosis at 52 weeks in the FAS. The same logistic regression described in Section 3.11.1.3 will be used for the analysis. Multiple imputation of missing NASH resolution status will be conducted before performing the logistic regression (see Section 3.11.1.3).

3.11.1.3. Methods for Multiple Imputations

For efficacy analyses relative to “treatment-regimen” estimand, the ICEs and the resulting missing values will be handled as follows:

There are no ICE for “treatment-regimen” estimand. If the endpoint biopsy is not collected, data from participants who discontinue, but with non-missing endpoint biopsy from the same treatment arm will be used to impute the missing value (retrieved dropout imputation). In cases where there are not enough retrieved dropouts to provide a reliable imputation model, the imputation of missing data will be done with the jump-to-reference (placebo) imputation approach.

For NASH resolution with no worsening of fibrosis which is a binary endpoint and multiple conditions (see Section 3.11.1) need to be satisfied in addition to no increase in fibrosis score, the imputation will be done for each of the components separately. That is, ballooning score, steatosis score, inflammation score, and fibrosis score will be imputed separately. At the end, the imputed values will determine if the participant satisfies all criteria to have “Yes” for NASH resolution with no worsening of fibrosis or “No” otherwise based on the criteria listed in Section 3.11.1.

The statistical inference over multiple imputation of missing data is guided by methodology proposed by Rubin (1987).

3.11.1.4. Additional Analyses of the Primary Outcome

In the event of patients dropping out before Week 36, primary analyses may be repeated using the EXAS for exploratory purposes. The model and details of analysis is similar to what is described in Section 3.11.1.1.

3.11.2. Secondary Efficacy Analyses

3.11.2.1. Analyses of Continuous Outcomes

Analyses for change from baseline in body weight as well as mean absolute change in liver fat content by MRI-PDFF will be conducted using data in the EAS from baseline through the 52-week visit with the aid of an MMRM. REML will be used to obtain model parameter estimates and the Kenward-Roger option will be used to estimate denominator degrees of freedom. The response variable of the MMRM model will be the primary measure and model terms of interest will include treatment, visit, treatment-by-visit interaction, baseline T2DM status (Yes/No), and region (Japan, US including Mexico, and Europe including Israel) as fixed effects, and baseline values of the dependent variable as a covariate. An unstructured covariance structure will be used to model the within-patient errors. If this model fails to converge, the following covariance structures will be tested in the following order:

1. Heterogeneous Toeplitz
2. Heterogeneous First Order Autoregressive
3. Heterogeneous Compound Symmetry
4. Toeplitz
5. First Order Autoregressive, and
6. Compound Symmetry.

The first covariance structure that converges will be used. The resulting least squares mean estimate of mean change from baseline of each outcome will be summarized by visit and by study treatment.

If the outcome has only the baseline and end-of-treatment measurements, the analysis will be conducted utilizing ANCOVA. The response variable will be the continuous outcome and model terms will include treatment, baseline T2DM status (Yes/No), and region (Japan, US including Mexico, and Europe including Israel) as fixed effects, and baseline values of the outcome as a covariate.

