# 9.4.3.2. Secondary Analyses

In addition to the primary efficacy analysis of NASH resolution with no worsening of fibrosis in study population, the following secondary study objectives will be analyzed on the EAS:

- Regression of fibrosis with no worsening of NASH at Week 52.
- Prevention of fibrosis progression at Week 52.
- Decreasing NAS by  $\geq 2$  points at Week 52.
- Decreasing liver fat content by MRI-PDFF at Week 52.
- Decreasing body weight at Week 52.

Analyses for regression of fibrosis with no worsening of NASH, prevention of fibrosis progression, and decreasing NAS by  $\geq 2$  points will be conducted in a manner similar to the primary efficacy analyses discussed in Section 9.4.3.1.

Decreasing liver fat content by MRI-PDFF and body weight will be analyzed by MMRM. The corresponding baseline value, treatment, visits, treatment by visit interaction, and stratification factors are the terms in the MMRM analysis.

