2.2. Determination of Sample Size

Sample size selection is guided by the objective of establishing superiority of each tirzepatide dose to placebo relative to the proportion of participants achieving NASH resolution without worsening of fibrosis at 52 weeks from randomization. The evaluation of superiority to placebo will be conducted for each of the 3 tirzepatide doses at 2-sided significance level of 0.05 using a test of 2 proportions. The power is assessed based on the following assumptions:

- the tirzepatide group mean response rate is assumed to be 42.5%
- the placebo group mean response rate is assumed to be 12.5%
- the dropout rate is assumed to be a 20%, and
- 1:1:1:1 randomization.

On the basis of these assumptions, approximately 196 participants will be required to provide at least 80% power to establish superiority of tirzepatide 5-mg, tirzepatide 10-mg, or tirzepatide 15-mg doses to placebo. This results in approximately 40 completers per arm. No adjustment for multiplicity will be performed.

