3.14. Safety Analyses

Unless specified otherwise, safety assessments will be based on the SS ([Table GPHR.3.1](#)). All events that occur between the date of first dose of study drug to the date of patient's safety follow-up visit or patient's end of study participation will be included, regardless of the adherence to study drug or availability of the end of treatment liver biopsy. For assessing the benefit and risk profile through 52 weeks, selected safety analyses will be conducted by utilizing safety data from first dose through the date of the 52-week visit.

The statistical assessment of homogeneity of the distribution of categorical safety responses among treatment arms will be conducted using Fisher's exact test, unless specified otherwise.

The mean change from baseline differences among treatments at all scheduled visits will be assessed via an MMRM using REML, unless specified otherwise. The model will include baseline T2DM status (Yes/No), the region (Japan, US including Mexico, and Europe including Israel), treatment group, visit and treatment-by-visit interaction as fixed effects, and baseline value of the safety parameter as a covariate. To model the covariance structure within patients, the unstructured covariance matrix will be used. If this model fails to converge, the covariance structures specified in Section [3.11.2.1](#) will be tested in order.

For selected safety parameters, time-to-first-event analysis via the Cox Proportional-Hazards model may be conducted. Patients without the event will be censored at the end of study participation. For patients experiencing the event, the "time-to-first-event" will be the time (in days) from first dose to first occurrence of the event.

Where necessary, the rate of events will be analyzed using a generalized linear mixed-effects model assuming the number of events follow a negative binomial distribution and with treatment as a fixed effect. The logarithm of days during the active treatment period will be adjusted as an offset to account for possible unequal treatment duration of follow-up between patients.

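### The body-weight MMRM shares one baseline slope across ten visits, so the Week 52 comparison is slightly less precise than it could be; a baseline-by-visit term is a cheap improvement

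*SAP*

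**What the plan says.** SAP 3.11.2.1 models change from baseline in body weight, and absolute change in liver fat by MRI-PDFF, with an MMRM. Its terms are treatment, visit, treatment-by-visit, T2DM status and region, with "baseline values of the dependent variable as a covariate". The covariance is unstructured unless that model fails to converge, and least squares means are reported by visit. Protocol 9.4.3.2 agrees: "The corresponding baseline value, treatment, visits, treatment by visit interaction, and stratification factors are the terms in the MMRM analysis". Neither text has a baseline-by-visit term.

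The Schedule of Activities (Protocol 1.3) measures weight after baseline at Weeks 4, 8, 12, 16, 20, 26, 32, 40, 48 and 52, which is ten visits. MRI is scheduled at Weeks 26 and 52 only.

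The optional treatment-regimen analysis of Week 52 weight (SAP 3.11.2.3) uses ANCOVA, where the baseline slope belongs to Week 52 alone.

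**The concern.** Weight loss builds up over an escalation of 4 to 20 weeks and continues afterwards. If loss in kilograms is roughly proportional to starting weight, the slope of change on baseline is near zero at Week 4 and clearly negative by Week 52. A model with one slope for all visits must compromise. With an unstructured covariance, generalised least squares gives most weight to the visits with the least residual variance, which are the early ones. The compromise then sits near the Week 4 slope.

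At stake is some precision for a secondary endpoint. There is also a small mismatch between the two estimands' analyses. The MMRM and the Week 52 ANCOVA adjust for baseline differently, so a gap between their results would partly reflect that difference rather than adherence or imputation.

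**Working it through.** **The plan's own figure.** The documents give no SD, standard error or power for body weight. The only stated size is for the primary endpoint (SAP 2.2): "approximately 196 participants will be required to provide at least 80% power", at a "2-sided significance level of 0.05 using a test of 2 proportions", with response rates of 42.5% and 12.5% and 20% dropout.
- Pooled rate 0.275: n = [1.96·√(2·0.275·0.725) + 0.842·√(0.125·0.875 + 0.425·0.575)]² / 0.30² = 33.6, so 34 per arm. With continuity correction it is 40.
- 4·40/0.8 = 200, close to 196. In the other direction, 196·0.8 = 156.8, the 157 evaluable participants of Protocol 1.1.
- The figure reproduces. It fixes 49 per arm (196/4) and 20% dropout for what follows.

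**Inputs for body weight**
- From Protocol 2.2: at Week 26, at least 5% loss in 50.0%, 77.3% and 85.7%, and at least 10% loss in 16.8%, 45.5% and 54.3%, for 5, 10 and 15 mg. Assuming normality, mean (SD) percent loss is 5.0 (5.2), 9.3 (5.8) and 10.6 (5.2).
- Assumed: placebo loss 1% (SD 5%), baseline mean 100 kg, baseline SD 15, 20 or 25 kg, loss proportional to baseline, Week 52 loss 1.0 or 1.4 times Week 26 loss, correlation 0.8 to 0.95 per 26 weeks, measurement SD 0.8 kg.

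**Expected Week 52 slope.** Under proportionality it is minus the average fractional loss over the four arms: (1 + 5.0 + 9.3 + 10.6)/4 = 6.5%, so about −0.065 kg/kg. With the 1.4 multiplier it is about −0.09.

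**Shared slope.** With visit slopes β and residual covariance S, the common slope is b = 1'S⁻¹β / 1'S⁻¹1. Both models were fitted by maximum likelihood to simulated trials (49 per arm, 20% monotone dropout, 150 trials per scenario):

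| Week 52 loss vs Week 26 | Baseline SD (kg) | Shared slope | Week 52 slope | Model SE, shared (kg) | Model SE, by visit (kg) | Ratio |
|---|---|---|---|---|---|---|
| 1.0 | 15 | −0.007 | −0.066 | 1.160 | 1.145 | 1.013 |
| 1.0 | 20 | −0.006 | −0.069 | 1.189 | 1.163 | 1.023 |
| 1.0 | 25 | −0.006 | −0.068 | 1.212 | 1.174 | 1.033 |
| 1.4 | 15 | −0.009 | −0.094 | 1.381 | 1.357 | 1.018 |
| 1.4 | 20 | −0.007 | −0.093 | 1.408 | 1.366 | 1.031 |
| 1.4 | 25 | −0.007 | −0.094 | 1.456 | 1.390 | 1.047 |

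The SEs are for 5 mg versus placebo; the other doses match closely. Empirical SE ratios ranged from 0.96 to 1.04, too noisy at 150 trials to use, so the model-based SEs are quoted.

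**Hand check.** SE ratio = √(1 + [(β₅₂ − b)·SD_baseline / SD_residual]²). For baseline SD 20 and residual SD 6: gap 0.0686 − 0.0062 = 0.0624, giving √(1 + (1.248/6)²) = 1.021, against 1.023 simulated.

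**Shift in a single trial.** The two models differ by about the slope gap times the chance baseline imbalance, whose SD is SD_baseline·√(2/49). A normal variable has mean absolute size 0.80 times its SD.
- Smallest case: 15·√(2/49) = 3.03 kg; × gap 0.0585 = 0.18; × 0.80 = 0.14 kg.
- Largest case: 25·√(2/49) = 5.05 kg; × gap 0.0868 = 0.44; × 0.80 = 0.35 kg.

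**Bias and power.** Mean estimates agreed within 0.06 kg. Power for 5 mg versus placebo was 91% to 100% under both models, differing by at most 1.3 points, within simulation error. For 10 and 15 mg it was 100% under both.

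**MRI-PDFF.** With assumed slopes from −0.30 to −0.50, baseline SD 6, residual SDs 4.5 and 5, and correlation 0.6 to 0.8, the SE ratio is 1.001 to 1.016.

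**The case against.** The strongest reply is that the model is valid under randomisation, protocol and SAP agree on it, and nothing a reader would conclude changes. That stands: this is a matter of efficiency, not an error.

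Three stronger readings are tempting, and the documents do not support them.
- **That baseline is hardly adjusted for at all.** The response is change from baseline, so subtraction has already done most of the work. With baseline SD 20 kg, slope −0.065 and residual SD 6 kg, the SD of raw Week 52 weight is 19.6 kg, of change 6.1 kg, and of the ANCOVA residual 6.0 kg. Subtraction removes over 99% of the baseline-related variance. The shared slope falls short only on what is left.
- **That a chance imbalance of about 4 kg between arms (20·√(2/49) = 4.0) goes uncorrected.** It is subtracted too. Only imbalance times slope gap remains, which is tenths of a kilogram.
- **That the loss amounts to discarding participants.** The trial is not sized on body weight, and simulated power barely moves.

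A reader might also extend the point to the safety MMRMs, which enter "baseline value of the safety parameter as a covariate". No gain was computed for them, and nothing in the documents shows that those slopes change over visits as weight's is expected to.

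The SAP also has partial cover. Percent change in weight (Table GPHR.3.2) should depend little on baseline if loss is proportional, and the Week 52 ANCOVA has its own slope. But percent change is exploratory and the ANCOVA is optional, so neither replaces the MMRM for this secondary endpoint.

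**Conclusion.** The point holds as a cheap improvement for body weight at Week 52. The shared slope recovers only about 14% to 21% of the variance reduction available on the change scale; for example, with baseline SD 15 kg and multiplier 1.0, 1 − (0.0585/0.0656)² = 20%. The SE is about 1% to 5% larger than needed. A single trial's estimate moves by about 0.15 to 0.35 kg on average, at most about a quarter of its SE (0.35/1.39). There is no bias and no material change in power.

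The mechanism follows from the specified terms and covariance, together with a baseline slope that steepens over time. The size depends on assumed weight SDs, correlations and proportional loss. A wider closed-form grid gave SE ratios from 1.001 to 1.159. The top value needs a pooled slope of −0.15, which means an average loss across all four arms, placebo included, above the 10.6% derived for the highest dose at Week 26.

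**What to change.** In SAP 3.11.2.1, add a baseline-by-visit interaction to the body-weight MMRM, so that the Week 52 comparison uses a Week 52 baseline slope, as the ANCOVA in SAP 3.11.2.3 does. It can be left out for MRI-PDFF.

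The cost is nine parameters (ten slopes instead of one) among about 196 participants, and no new data. The model is slightly heavier to fit, beside an unstructured covariance that already has 10·11/2 = 55 parameters. The existing fallback sequence of covariance structures covers non-convergence. Protocol 9.4.1 lets a change that is not a principal feature be recorded and justified in the SAP, so an amendment should not be needed. The term should be specified before unblinding, so that the two models are not compared with results in hand.

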#### 8.1.2.2. Liver Fat Content Determined from Magnetic Resonance Imaging

As part of the magnetic resonance imaging (MRI) evaluation, liver fat content will be determined using MRI – Proton Density Fat Fraction (MRI-PDFF). The fat fraction is the proportion of mobile protons in liver tissue attributable to fat, and is a noninvasive MRI-based biomarker of liver triglyceride concentration.

Participants will undergo 3 liver-directed MRI evaluations as outlined in the SoA (Section 1.3). MRI images will be transmitted to a central reader for evaluation of the MRI-based efficacy endpoints. For patient safety, images should also be over-read locally to assure there are no underlying liver pathologies other than NASH.

In the event of early termination from the study drug or the study,

- the second MRI exam may be performed when
  - o the participant has been on treatment for at least 16 weeks, and
  - o within 2 weeks of treatment discontinuation

- the third MRI exam may be performed
  - o when the participant has been on treatment for at least 36 weeks, and
  - o within 2 weeks of treatment discontinuation

MRIs will be performed after a fast of at least 6 hours. Participants are allowed to take necessary medications and small quantities of water during the fast. Additional exclusion criteria apply for MRI examination eligibility, which do not count toward eligibility for study participation. These exclusions are:

- a contraindication to MRI examinations
- extreme claustrophobia
- weight or girth exceeds the scanner capabilities
- any condition or circumstance that, in the opinion of the investigator, would interfere with completion of MRI examinations

For patients with claustrophobia in MRI machines, investigators may offer, at their discretion, a light sedative. However, if the patient is not willing to attempt MRI with light sedation, the patient should be excluded from the MRI evaluation but should not be excluded from the study.

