1.2. Secondary Objectives

The secondary objectives are to demonstrate that tirzepatide 5 mg, 10 mg, or 15 mg administered SC QW is superior to placebo at Week 52 for:

- Regression of fibrosis with no worsening of NASH with respect to proportion of participants with ≥ 1 -point decrease in fibrosis stage with no worsening of NASH on liver histology from baseline.
- Prevention of fibrosis progression measured with respect to proportion of participants with ≥ 1 -point increase in fibrosis stage on liver histology from baseline.
- Decreasing NAFLD Activity Score (NAS) by ≥ 2 points with respect to proportion of participants that achieve a ≥ 2 -point decrease in NAS on liver histology, with ≥ 1 -point reduction in at least 2 NAS components (steatosis, hepatocellular ballooning, lobular inflammation) from baseline. The NAS is based on the definition proposed by the NASH Clinical Research Network. The score is defined as the unweighted sum of the scores for steatosis (0-3), lobular inflammation (0-3), and ballooning (0-2); thus ranging from 0 to 8 (Kleiner et al. 2005).
- Decreasing liver fat content with respect to mean absolute change in liver fat content by MRI-PDFF.
- Decreasing body weight with respect to mean change in body weight from baseline.

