3.2. General Considerations

Statistical analysis of this study will be the responsibility of Eli Lilly and Company (Lilly) or its designee. All statistical analyses will be conducted with SAS Version 9.4 or higher unless otherwise stated. Some analyses and summaries described in this analysis plan may not be conducted if not warranted by data (e.g., few events to justify conducting an analysis). Listings of events will be provided in such situations. Additional analyses of the data may be conducted as deemed appropriate without further changes made to the protocol or SAP, even after the primary or final database locks.

Additionally, to avoid potential selection biases, unless stated otherwise, statistical summaries and analyses will be conducted based on randomized study treatment group regardless of the actual treatment received by the patient. Unless otherwise noted, all tests of treatment effects will be conducted at a 2-sided alpha level of 0.05, and the CI will be calculated at 95%, 2-sided. In statistical summaries and analyses, patients will be analyzed as randomized.

For histological, imaging, and TE measurements the last available data during Visit 1 to Visit 3 prior to or within 1 week after the first study drug administration will serve as baseline. For patients who have an eligible historical biopsy within 6 months of Visit 1, the historical biopsy will serve as baseline for histological measures. Unless specified otherwise, the last measurement during Visit 1 to Visit 3 (including unscheduled visits) collected prior to or on the first dose day will serve as baseline. For immunogenicity, data collected up to the first dose time will serve as baseline. For laboratory and ECG, baseline needs to be prior to or within 1 hour after the first dose time. For PROs, data collected at Visit 3, regardless of the timing relative to the first dose, will serve as baseline.

There will be 2 estimands of interest in evaluating the primary and secondary efficacy objectives. The first estimand, the “efficacy” estimand, represents efficacy prior to discontinuation of study drug.

Primary Estimand (efficacy estimand)

The primary clinical question of interest is: What is the treatment difference in NASH resolution without worsening of fibrosis after 52 weeks of treatment assuming all participants who meet the inclusion criteria would have completed the treatment period?

The “efficacy estimand” is described by the following attributes:

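### If the unstructured weight MMRM fails to converge, the fallback rule keeps model-based errors, so the Week 52 test can exceed 5%, by an amount that depends on the true covariance

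*SAP*

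**What the plan says.** SAP 3.11.2.1 covers the two continuous secondary endpoints, body weight and liver fat by MRI-PDFF. The model is fitted by REML, and "the Kenward-Roger option will be used to estimate denominator degrees of freedom". For the covariance, "An unstructured covariance structure will be used to model the within-patient errors". If the fit does not converge, six alternatives follow in fixed order. The list opens with "1. Heterogeneous Toeplitz", then heterogeneous AR(1) and heterogeneous compound symmetry, and then the homogeneous versions of Toeplitz, AR(1) and compound symmetry. The choice rests on convergence alone: "The first covariance structure that converges will be used".

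Table GPHR.3.2 sends several exploratory outcomes to the same model, including waist circumference, percentage weight change, liver enzymes and biomarkers. Section 3.14 carries the list to the general safety MMRM: "If this model fails to converge, the covariance structures specified in Section" 3.11.2.1 are to be tried in order. Section 3.2 sets the level: "all tests of treatment effects will be conducted at a 2-sided alpha level of 0.05", unless otherwise noted.

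Neither document names a robust variance. Neither gives an SD or correlation for weight change, a probability of non-convergence, or an error rate under the fallback.

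**The concern.** The secondary objective concerns "Decreasing body weight with respect to mean change in body weight from baseline" at Week 52. When the unstructured model is replaced, the standard error of the Week 52 contrast comes from the replacement structure, whether or not that structure describes the data.

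- **Homogeneous structures (positions 4 to 6)** impose one variance on all visits. If the spread of weight change widens over time, the Week 52 variance is averaged down towards the early visits.
- **Heterogeneous Toeplitz and AR(1) (positions 1 and 2)** give each visit its own variance but force the same correlation on all pairs of visits equally far apart in the sequence. Weight visits are 4 to 8 weeks apart. If later visits are more strongly correlated than early ones at the same lag, the fitted Week 52 variance can also come out too small.

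Kenward-Roger adjusts precision and degrees of freedom within the assumed structure, so it does not correct either problem. At stake are an interval that is too narrow and a p-value that is too small for a secondary endpoint, only in the situation for which the rule is written.

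**Working it through.** **Inputs from the documents.** The Schedule of Activities (Protocol 1.3) has ten on-treatment postbaseline weights: Weeks 4, 8, 12, 16, 20, 26, 32, 40, 48 and 52. An unstructured matrix then has 10 × 11 / 2 = 55 parameters. For MRI, "Participants will undergo 3 liver-directed MRI evaluations", so there are two postbaseline scans and 2 × 3 / 2 = 3 parameters. There are 196 / 4 = 49 randomized per arm, with 20% dropout assumed (SAP 2.2). The level is two-sided 0.05.

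**Inputs assumed.** The true covariance of weight change. A partial anchor is in Protocol 2.2, which gives 26-week proportions losing at least 5% and at least 10% of weight in the earlier Phase 2 trial. Under normality, SD = 5 / (z for the 5% proportion − z for the 10% proportion):

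- 5 mg (50.0%, 16.8%): 5 / (0 + 0.96) = 5.2 percentage points
- 10 mg (77.3%, 45.5%): 5 / (0.75 + 0.11) = 5.8
- 15 mg (85.7%, 54.3%): 5 / (1.07 − 0.11) = 5.2

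At an assumed 90 to 100 kg this is about 4.7 to 5.8 kg at Week 26. It says nothing about other visits or about correlations.

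**The plan's own figure.** The only stated error rate is 5%. In 1,500 simulated complete-data trials at 40 per arm, the unstructured model rejected 4.5% of the time, as it should.

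**Formula.** Each fallback is fitted to its large-sample limit under a given true covariance. Then

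type I error = 2 × [1 − Φ(1.96 × √(model variance / true variance))] for the Week 52 contrast.

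**Worked example.** The assumed truth is a random slope plus Brownian motion plus 0.8 kg measurement error, with SD rising from 1.7 kg at Week 4 to 8 kg at Week 52 (true Week 52 variance 64.6).

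- Heterogeneous Toeplitz: fitted 40.6; √(40.6/64.6) = 0.79; 1.96 × 0.79 = 1.55; error 12%
- Heterogeneous compound symmetry: fitted 62.2; √(62.2/64.6) = 0.98; error 5.4%
- Compound symmetry: fitted 26.4; √(26.4/64.6) = 0.64; error 21%

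The square root is also the ratio of interval widths, so the first interval is about 21% too narrow and the last about 36%.

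**Wider range.** Eight assumed covariances were used, with Week 4 SD 1.6 to 4.2 kg and Week 52 SD 6.8 to 7.8 kg, each with complete data and with 20% random dropout. Three were also simulated (400 trials each, 49 per arm, 20% dropout; Monte Carlo standard error about 1 to 2 points).

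| Position and structure | Large-sample range | Simulated: random slope | Simulated: random walk | Simulated: heterogeneous AR(1) truth |
|---|---|---|---|---|
| 1 Heterogeneous Toeplitz | 3.9% to 13.6% | 15% | 9% | 3% |
| 2 Heterogeneous AR(1) | 3.9% to 13.0% | 14% | 9.5% | 3% |
| 3 Heterogeneous compound symmetry | 3.8% to 6.7% | 8% | 5% | 3% |
| 4 Toeplitz | 11.0% to 20.2% | not run | not run | not run |
| 5 AR(1) | 11.0% to 21.0% | not run | not run | not run |
| 6 Compound symmetry | 11.9% to 26.5% | 29% | 18.5% | 20% |

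The low end for positions 1 and 2 arises where SDs grow and correlation decays with time. There the model variance is up to 1.11 times the true one, and √1.11 × 1.96 = 2.06 gives 3.9%.

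**MRI-PDFF.** With two visits, each heterogeneous structure has two variances and one correlation. That is the unstructured matrix, apart from limits on the sign of the correlation.

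**The case against.** The strongest reply is that this is a prespecified ordered list with the flexible structures first, which is common practice and prevents choosing a structure by its result. It acts only if the unstructured model fails, and about 157 completers against 55 parameters do not by themselves suggest failure. The homogeneous structures need four successive failures: unstructured and then all three heterogeneous forms. Weight is a secondary endpoint in a Phase 2 trial with no multiplicity control (SAP 3.6). Protocol 4.3 already reports clinically relevant weight loss against placebo at all three doses, so an exactly true null is implausible and interval width is the practical issue. SAP 3.11.2.3 also allows a Week 52 ANCOVA for the treatment-regimen estimand, which needs no repeated-measures covariance.

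All of this stands, and it keeps the point minor. It does not answer the narrower criticism that convergence is not evidence of fit and that nothing in the plan protects the standard error once the structure is wrong.

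A reader might infer more than the documents support:

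- **That the fallback inflates error to 10% or more in general.** Such figures come from particular assumed covariances. The first fallback can be at or below nominal, and heterogeneous compound symmetry stays close to it.
- **That safety results are affected to the same degree.** No safety variable was computed, and nothing in the documents shows that laboratory or vital-sign changes grow in variance as weight change may. The pancreatic-enzyme and vital-sign models (SAP 3.14.3.3.1 and 3.14.6) are written out without the fallback list.

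**Conclusion.** The point holds as a conditional one. If the unstructured weight model fails, the plan's rule can give a Week 52 test above its nominal 5%. Depending on the true covariance, the level is about 4% to the mid-teens under heterogeneous Toeplitz or AR(1), near nominal under heterogeneous compound symmetry, and about 11% to 27% under the homogeneous structures in large-sample limits (29% in one simulation of compound symmetry).

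These figures rest on assumed SDs and correlations. The homogeneous results also rest on variance growing over visits. That is plausible, because change is zero at baseline, entry requires stable weight (Protocol 5.1, criterion 8) and dose escalation runs to Week 20 in the 15 mg arm, but the documents do not establish it. The probability of reaching any fallback is unknown and may be small. MRI-PDFF is essentially unaffected. This is a cheap improvement to the SAP and not a threat to the trial's main conclusions.

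**What to change.** Add to SAP 3.11.2.1: *If any structure other than unstructured is used, standard errors will be the empirical (sandwich) estimates with between-within degrees of freedom in place of Kenward-Roger.* Carry the sentence to the analyses that refer to this list, namely the MMRM rows of Table GPHR.3.2 and Section 3.14. The ordered list can stay.

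The cost is one sentence and one procedure option, used only when the fallback is triggered. With a robust variance the large-sample level is 5% by construction; this was not simulated. There are two downsides. At about 40 to 49 per arm, sandwich errors are somewhat less stable and slightly liberal. They also correct only the standard error: if dropout depends on earlier weights and the working structure is wrong, the point estimate can still be biased.

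Switching to the Week 52 ANCOVA is not recommended as the fallback. It drops participants without a Week 52 value and so changes how missing data are handled under the hypothetical efficacy estimand.
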